## INTERVENTION PROTOCOL

From the following scheme (Scheme 3), each training session of the muscle strengthening program was structured for each of the intervention groups, which was based on the principles of training and the Earl and Hoch protocol described in the theoretical framework.

*Scheme 3: A y B Strengthening Program*

After the adjustments described in the pilot test, the strengthening program was applied to the forty patients who were previously randomized to the intervention protocols for groups A and B.

Each of the exercise sessions lasted approximately 45 to 60 minutes, of which, the first 8 to 10 minutes were dedicated to the initial warm-up exercises, the same for program A and B, which gave way to the phase central to the session, that is to say the strengthening exercises: group B took about five minutes less to complete it, because they performed an exercise less than group A in each of the three phases set out in the program; This phase of strengthening lasted approximately 20 to 30 minutes of the total session.

Each session was divided into four parts, of which the second part (central strengthening phase) included between 24 and 28 exercises in total, group A and B respectively. In addition to this, the anatomical conditioning phase was carried out in two weeks, in which 5 to 6 strengthening exercises were prescribed depending on the treatment group, but for both groups the volume was two sets of 10 repetitions, with approximately 30 seconds rest between sets and between exercises, with an execution speed of 1/1 (concentric / eccentric contraction ratio) that allowed patients to adapt to adequate movement control and therefore, joint protection.

After the conditioning phase, from the third to the sixth week of intervention, the strengthening or resistance strength gain phase was performed, in which 6 to 7 exercises were performed; that is, the training was progressed with the addition of an exercise and also with the increase of series and repetitions as follows: from the third to the fifth week the volume was 2 sets of 15 repetitions, with a 20 seconds rest and a 2/2 contraction speed, which allowed greater control of the movement by decreasing the speed of execution of the movement; In the sixth week the participants went from performing two sets of 15 repetitions to performing 3 sets of 15 repetitions, with a decrease in rest between sets and exercises of 10 seconds and a decrease in contraction speed (ratio 3/3) that implied greater neuromuscular control over the exercise performed and therefore significant increases in muscle strength.

During the last two weeks of treatment, both groups increased the number of exercises (7 exercises group B and 8 exercises group A) and some of the exercises changed to exercises of greater difficulty, but with a decrease in the volume of training in the seventh week (two sets of 10 repetitions for session 21 and two sets of 15 repetitions for sessions 22 and 23) and this increase in the eighth and final week of training (three sets of 15 repetitions). The reason for these changes was based on the principles of progression and overload, as well as on ensuring the correct execution of the exercises without compensation from other muscle groups, especially the lumbar muscles, and also to avoid premature fatigue observed in the pilot test.

Therapeutic Effect of Two Muscle Strengthening Programs in Patients with Patellofemoral Pain Syndrome

The warm-up included 13 exercises, performed in an average time of 8 to 10 minutes and in the same way during the eight weeks of intervention, while, in the fourth part of the session, final stretching or return to calm, the participants performed 8 exercises during the first 6 weeks of intervention and 10 exercises in the last two weeks. Each exercise was performed for 30 seconds, which took approximately 8 to 10 minutes to complete them. Finally, the neuromuscular component (static balance training with one-foot balance exercises) was performed after muscle strengthening exercises. It was based on 8 exercises, which changed every two weeks with a duration between 30 to 45 seconds each, and between one to two repetitions per exercise depending on the week of intervention. The three phases mentioned above were exactly the same for both treatment groups.

All participants participated in groups of four people per session, three exercise sessions per week for eight weeks in total, at the IPS-CAFAM (Institución Prestadora de Salud de la Caja de Compensación Familiar) Rehabilitation Center, for a total of twenty-four sessions, which were supervised by a Physiotherapist, who was responsible not only to verify the quality in the performance of each of the exercises, but to teach during the first two weeks of intervention (anatomical conditioning phase) the fundamental bases of adequate breathing and feed them back during all the intervention protocol, as well as guaranteeing a correct posture in performing the training and thus avoiding the appearance of low back pain as a result of a poor training technique, as well as the increase in intra-abdominal pressure generated by the “pushing” when it is not known to breathe properly during strength training.

The hydration of each participant was also crucial during each training session. Similarly and prior to the start of the protocol, all patients were instructed and suggested the importance of wearing appropriate footwear for training (sports sneakers, sportswear - during the first two weeks they were suggested to wear shorts to observe the position of the knees during the exercises and later the use of liquefied pants up to the ankle to avoid rubbing the elastic bands with the skin-; likewise, they were instructed to bring water bottle, towel to dry the sweat and not to use elements that could injure them during the exercise, such as bracelets or necklaces.

Therapeutic Effect of Two Muscle Strengthening Programs in Patients with Patellofemoral Pain Syndrome

However, it is important to mention that it was agreed with about 15% of the patients residing in sites far from the place where the program was carried out, at least two of the three sessions in the rehabilitation center, and the third session at home, taking into account that it was important to supervise the performance of the exercises by the Physiotherapist in charge of the intervention program. To do this, the participants attached the necessary evidence in the form of photos and videos to support their commitment in carrying out the exercises. This aspect was controlled throughout the time by the physiotherapist.

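### Do the conflicting exercise totals and session numbers in the intervention text call for a change to the plan?

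*Protocol*

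**What the plan says.** All the programme figures are in the Protocol, section Intervention Protocol.

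- **Exercise totals.** In a sentence about the make-up of each session, the strengthening part "included between 24 and 28 exercises in total, group A and B respectively".
- **Direction of the difference.** The paragraph before explains group B's shorter strengthening time (about five minutes less): "they performed an exercise less than group A in each of the three phases set out in the program".
- **Counts by phase.** Conditioning, weeks 1 and 2: "in which 5 to 6 strengthening exercises were prescribed depending on the treatment group". Strength gain, "from the third to the sixth week of intervention": "in which 6 to 7 exercises were performed". Weeks 7 and 8: "7 exercises group B and 8 exercises group A".
- **Late volume.** There is "a decrease in the volume of training in the seventh week", detailed as "two sets of 10 repetitions for session 21 and two sets of 15 repetitions for sessions 22 and 23". Week 8 then rises to three sets of 15.
- **Timetable.** Three sessions a week for eight weeks, 24 in all.

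The section also says that warm-up, balance work and final stretching were identical in the two groups.

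**The concern.** Strengthening is the only part of the session that differs between the arms, so its description defines the comparison. Read literally, the totals give the larger number of exercises to B, the arm without the core work. That is the opposite of what the rest of the section says. The totals also cannot be counts for one session, because no session has more than 8 strengthening exercises, and the text does not say what they do count.

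The session numbers conflict with the timetable. Sessions 22 and 23 have one volume if the reader goes by session number and another if the reader goes by week. Session 21 is also affected, because week 7 itself contains two volumes. Sessions 19 and 20 have no volume by number.

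At stake is whether a reader could report or repeat the programme exactly, and whether the error reaches the comparison of A with B.

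**Working it through.** **1. Exercise totals**

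Inputs from the Intervention Protocol section: 5 or 6 exercises in weeks 1 and 2, 6 or 7 in weeks 3 to 6, and 7 (B) or 8 (A) in weeks 7 and 8. B always has one fewer, so A has 6, 7, 8 and B has 5, 6, 7.

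The stated pair is A 24, B 28. The per-phase counts give:

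| Counting unit | A | B |
|---|---|---|
| Once per phase | 6 + 7 + 8 = 21 | 5 + 6 + 7 = 18 |
| Once per week | 2×6 + 4×7 + 2×8 = 56 | 2×5 + 4×6 + 2×7 = 48 |
| Once per session | 6×6 + 12×7 + 6×8 = 168 | 6×5 + 12×6 + 6×7 = 144 |
| Once per two-week block | 6 + 7 + 7 + 8 = 28 | 5 + 6 + 6 + 7 = 24 |

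None of these four units reproduces the stated pair in its stated order, and A exceeds B in all of them. The two-week block gives the same two numbers with the arms exchanged, which suggests swapped labels. That is an inference: the only two-week change the text states is for the balance exercises.

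Distinct exercises are a further possible unit. The text does not allow that count. However, the SAP (Post-Intervention Results) describes core work added to hip and knee work that was done in the same way in both groups. That description does not suggest more exercises in B.

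**2. Session numbers**

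With three sessions a week, week w holds sessions 3w − 2 to 3w. Week 7 is therefore sessions 19 to 21 and week 8 is sessions 22 to 24, and 3 × 8 = 24 agrees with the stated total. Taking 21 to 23 as week 7 would put 20 sessions in the first six weeks (6 × 3 = 18 are available) and leave one for week 8.

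The week reading below keeps the stated order of volumes within week 7.

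| Session | By session number | By week and order |
|---|---|---|
| 19 | none given | 2×10 |
| 20 | none given | 2×15 |
| 21 | 2×10 | 2×15 |
| 22 | 2×15 | 3×15 |
| 23 | 2×15 | 3×15 |
| 24 | none given | 3×15 |

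The sizes of the conflict are:

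- Session 21: 2×10 = 20 against 2×15 = 30 repetitions per exercise. Per session this is 8×20 = 160 against 8×30 = 240 in A, and 7×20 = 140 against 7×30 = 210 in B.
- Sessions 22 and 23: 2×15 = 30 against 3×15 = 45 repetitions per exercise. Per session this is 8×30 = 240 against 8×45 = 360 in A, and 7×30 = 210 against 7×45 = 315 in B.

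The text gives these volumes without distinguishing the arms. The ratio of A to B is therefore the same on either reading: 160/140 = 240/210 = 360/315 = 8/7.

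**3. Use in the analysis**

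The SAP compares changes in the outcomes between groups (Mann-Whitney), changes within groups (Wilcoxon), baseline categories (chi-square or Fisher) and correlations (Spearman). Tables 5 to 10 contain clinical measurements only. Neither an exercise count nor a training volume enters any of them.

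**The case for a change.** The best case for acting is that this is a public description of the only component separating the arms, and it contradicts itself in running prose, so poor text extraction is not the cause. A reader who takes the totals at face value gets the arms the wrong way round. A team repeating the programme cannot tell what was done in the last two weeks. Scheme 3, which sets out the sessions, is not in the text available here and may hold the right layout, but the prose would still disagree with itself. Correction would cost little.

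The contradictions stand, and so does the point about replication. The documents do not settle whether the session numbers or the week labels are wrong, and only the investigator can say which volumes were used. The Protocol mentions photo and video evidence for home sessions (about 15% of patients) but no log of volume per session, so whether records exist to resolve it is unknown.

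What does not stand is any effect on the comparison. The direction of the difference is stated correctly in the paragraph before the totals and again, by arm, for the last phase. Totals by arm can be rebuilt from the per-phase counts. Only the meaning of 24 and 28 is lost.

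**Conclusion.** These are two clerical slips, and correcting them would bring no analytic gain. The arm order of 24 and 28 conflicts with the per-phase counts under each of the four units computed. Sessions 21 to 23 conflict with the timetable, by 10 repetitions per exercise in session 21 and 15 in each of sessions 22 and 23. The repetition gaps are differences between two readings and are not evidence of what was delivered.

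The passages must be reconciled with each other, with Scheme 3 and with any session records wherever the programme is reported. This review takes no view on which volume is right. That is a matter of description: the programme has already been delivered, and nothing in the randomised comparison, the tests or the conclusions changes with the answer.

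This rests on two assumptions: that B's counts are the lower of each stated pair, as the text says, and that the late volumes applied equally to both arms, as the text implies by not separating them.

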[name]

NCT04011436

Therapeutic Effect of Two Muscle Strengthening Programs in Patients with Patellofemoral Pain Syndrome

**Therapeutic Effect of Two Muscle Strengthening
Programs in Patients with Patellofemoral Pain
Syndrome from Bogota, Colombia.
Experimental Study, Clinical Controlled Trial.**

NCT: 04011436

Date of creation: July 1, 2018.

PROCESSING AND DATA ANALYSIS.

For the classification and verification of the information, the database was refined by recoding and labeling the variables necessary for the analysis, in addition, the variables that required it were converted to alphanumeric format and the review of extreme non-plausible data was performed. For the continuous variables in which two attempts were made as balance and plate a new variable was generated with the average of the measurements and in this way obtain the final result for the analyzes.

Univariate Analysis

The report of absolute and relative frequencies was made; the qualitative variables were presented in proportions and 95% confidence intervals. The normality of the continuous variables was evaluated by scatter plots (histograms, Kernel density and Q-Norm) and the numerical test of Shapiro-Wilk, and according to their distribution they were reported as means and standard deviations, when they had a distribution normal, or on the contrary, as medians and interquartile ranges.

Bivariate Analysis

In the bivariate analysis, a comparison of each of the Kujala test domains was initially performed to assess pain in the baseline, assessing the differences between the intervention groups using the chi-square or Fisher's exact tests. Additionally, the Spearman correlation coefficient was used to evaluate the relationship between two continuous variables, such as the Q angle and the anterior knee pain, evaluating the correlation in a marginal and conditioned way to each of the treatment groups.

Later, to evaluate if there were differences between the groups of treatment after the intervention on the variables of interest, deltas were generated from the Kujala test, EVA, number of squats, Q angle, balance, physical activity and core strength. with iron and trunk extension, evaluating normality by means of graphic and numerical methods. For the analysis of the differences of medians between the groups, taking into account that the outcomes did not present a normal distribution, and assuming the assumption of independence of the variables, we proceeded to use the non-parametric Mann-Whitney U test. Finally, through the Wilcoxon test, intragroup differences were evaluated for strength, pain and physical activity components.

The hypothesis tests were presented in two tails with an alpha of 0.05 and all the analyzes were executed with the statistical program STATA version 14.0.

BASELINE:

Study population

Therapeutic Effect of Two Muscle Strengthening Programs in Patients with Patellofemoral Pain Syndrome

Table 5 describes the general characteristics of the study population at baseline. There were no significant differences between the two intervention groups (A and B), which means that the randomization was adequate; however, in the total score of the Kujala test there was a difference of 12.5 points between the groups, with a lower score for group B (53.0), which indicates better core strength for these patients. Finally, the sex variable was defined as categorical and the rest of the variables as continuous, for which the medians and their respective interquartile range (IR) are reported, taking into account that the variables did not have a normal distribution.

Table 5: Baseline variables of the study population

Variables	Treatment A (n 20) Medium (RI)	Treatment B (n 20) Medium (RI)	Value p ^a
Sex * (Male, Ref)			
Female	90 (65.7-97.6) *	90.0 (65.7-97.6) *	1,000 ^b
Age	32.5 (25.5-38.0)	29.0 (25.0-36.5)	0,569
Initial weight (Kg)	64.6 (55.3-72.4)	62.7 (52.9-68.5)	0.379
Size (cm)	160 (156.5-167.0)	159.5 (154.0-163.0)	0.423
IMC	25.4 (21.5-27.9)	23.8 (22.3-25.2)	0.456
% of fat	35.4 (28.9-40.4)	35.4 (24.5-38.7)	0,714
% muscle	26.9 (24.5-28.9)	26.2 (24.6-29.0)	0.849
Visceral fat	6 (3.5-7.09)	5 (4.0-6.0)	0.433
IPAQ (minutes)	3003 (1116-4638)	1617 (944-6138)	0,588
Pain	7.5 (5.5-9.0)	7.0 (5.5-8.5)	0.764
Kujala total score	65.5 (42.5-72.5)	53.0 (44.5-71.5)	0,892
Q angle			
Straight	19.0 (15.0-20.0)	18.0 (15.0-20.0)	0,557
Left	18.0 (15.0-20.0)	18.0 (15.0-20.0)	0.944
Prone iron (seconds)	20.5 (12.0-32.0)	30.0 (13.5-33.5)	0.673
Side iron (seconds)			

Therapeutic Effect of Two Muscle Strengthening Programs in Patients with Patellofemoral Pain Syndrome

Right	15.0 (10.0-21.0)	15.0 (9.5-20.0)	1,000
Left	12.5 (10.5-19.0)	18.0 (11.0-23.0)	0.356
Trunk extension (seconds)	13.5 (6.0-26.5)	13.5 (2.5-20.0)	0,586
Squats	10.0 (8.0-18.5)	12.5 (8.5-20.0)	0.673

* percentage (95% CI); a: U from Mann-Whitney; b: Chi square test

In **Table 6**, with a 95% confidence, the values are expected to oscillate in a narrow range: thus, a statistically significant difference was not found for the domains contemplated by the Kujala test for the two treatment groups, except for the squat domain with a p of 0, 028. However, it can be seen that within the thirteen domains contemplated by the Kujala test, it was found that these results agree with what was found for the total score of the test in the baseline, highlighting that in the pain domain, the "occasionally severe" response option was greater for group B; likewise, they were for the domains of "severe atrophy", "pain with the support of the limb", "going up and down stairs", "sitting with knees bent", especially if you have exercised before, as well as for the most painful movements of the patella with daily activities and severe pain always when running. The score was only greater in group A for the domains of inflammation every night and severe deficiency for knee flexion.

Kujala

Table 6: Distribution of the 13 domains of the Kujala Questionnaire by intervention group in the baseline.

Domain	Treatment A (n = 20) % (95% CI)	Treatment B (n = 20) % (IC95%)	Value p *
Pain			0.506 ^a
Constant and severe	20.0 (7.2-44.3)	20.0 (7.2-44.3)	
Occasionally severe	20.0 (7.2-44.3)	40.0 (20.5-63.2)	
Interferes with sleep	10.0 (2.31-34.2)	10.0 (2.31-34.2)	
Mild and occasional	50.0 (28.3-71.6)	30.0 (13.4-54.1)	
Inflammation			0.108 ^b

Therapeutic Effect of Two Muscle Strengthening Programs in Patients with Patellofemoral Pain Syndrome

Permanently	10.0 (2.31-34.2)	20.0 (7.2-44.3)	
Every night	15.0 (4.5-39.2)	-	
With daily activities	30.0 (13.4-54.1)	10.0 (2.31-34.2)	
After great effort	30.0 (13.4-54.1)	30.0 (13.4-54.1)	
Do not	15.0 (4.5-39.2)	40.0 (20.5-63.2)	
Atrophy			0.451 ^b
Severe	-	5.0 (0.6-30.6)	
Mild	15.0 (4.5-39.2)	25.0 (10.2-49.3)	
Do not	85.0 (60.7-95.4)	70.0 (45.8-86.5)	
Limp			0.890 ^a
Constantly	10.0 (2.31-34.2)	10.0 (2.31-34.2)	
A little, sometimes	80.0 (55.6-92.7)	75.0 (50.6-89.7)	
Do not	10.0 (2.31-34.2)	15.0 (4.59-39.2)	
Limb support			0.347 ^b
Impossible to support	10.0 (2.31-34.2)	5.0 (0.6-30.6)	
Pain with support	55.0 (32.4-75.6)	80.0 (55.6-92.7)	
Completely painless	35.0 (16.9-58.7)	15.0 (4.59-39.2)	
Walk			1,000 ^b
Can not	5.0 (0.6-30.6)	5.0 (0.6-30.6)	
Between 1-2 Km	20.0 (7.2-44.3)	25.0 (10.2-49.3)	
More than 2 Km	45.0 (24.3-67.5)	45.0 (24.3-67.5)	
Unlimited	30.0 (13.4-54.1)	25.0 (10.2-49.3)	
Up and down stairs			0.050 ^b
Can not	5.0 (0.6-30.6)	-	

Therapeutic Effect of Two Muscle Strengthening Programs in Patients with Patellofemoral Pain Syndrome

Pain when going up and down	50.0 (28.3-71.6)	75.0 (54.9-95.0)	
Slight pain when going down	45.0 (24.3-67.5)	15.0 (4.59-39.2)	
Without difficulty	-	10.0 (2.31-34.2)	
Squats			0.028^b
Can not	20.0 (7.2-44.39)	-	
With help	5.0 (0.6-30.6)	15.0 (4.59-39.2)	
It is always painful	20.0 (7.26-44.3)	40.0 (20.5-63.2)	
Doing them quickly hurts	25.0 (10.2-49.3)	40.0 (20.5-63.2)	
Without difficulty	30.0 (13.4-54.1)	5.0 (0.6-30.6)	
Remain seated with knees bent	0.236 ^b		
Unable to do it	15.0 (4.59-39.2)	-	
Pain forces the knees to extend	65.0 (41.2-83.0)	70.0 (45.8-86.5)	
It is always painful	10.0 (2.31-34.2)	10.0 (2.31-34.2)	
There is only pain if you have exercised	5.0 (0.6-30.6)	20.0 (7.26-44.3)	
There is no problem	5.0 (0.06-30.6)	-	
Painful movements of the kneecap	0.303 ^b		
More than two dislocations	10.0 (2.31-34.2)	10.0 (2.31-34.2)	
Less than a confirmed dislocation	10.0 (2.31-34.2)	15.0 (4.59-39.2)	
Occasionally with everyday activities	20.0 (7.26-44.36)	40.0 (20.5-63.2)	
Occasionally with exercise	30.0 (13.4-54.1)	30.0 (13.4-54.1)	
Do not	30.0 (13.4-54.1)	5.0 (0.6-30.6)	
Deficiency for knee flexion	0,227 ^b		
Severe	20.0 (7.26-44.3)	5.0 (0.06-30.6)	
Mild	70.0 (45.8-86.5)	70.0 (45.8-86.5)	

Therapeutic Effect of Two Muscle Strengthening Programs in Patients with Patellofemoral Pain Syndrome

[figure not shown]
Do not	10.0 (2.31-34.2)	25.0 (10.2-49.3)	
Run			0.512 ^b
Be unable	25.0 (10.2-49.3)	15.0 (4.59-39.2)	
Severe pain always	-	15.0 (4.59-39.2)	
Mild pain from the start	25.0 (10.2-49.3)	25.0 (10.2-49.3)	
Pain after 2 Km	35.0 (16.9-58.7)	35.0 (16.9-58.7)	
Unlimited	15.0 (4.59-39.2)	10.0 (2.31-34.2)	
Skip			0.915 ^b
Be unable	25.0 (10.2-49.3)	30.0 (13.4-54.1)	
With permanent pain	15.0 (4.59-39.2)	20.0 (7.26-44.3)	
With slight difficulty	35.0 (16.9-58.7)	35.0 (16.9-58.7)	
Without difficulty	25.0 (10.2-49.3)	15.0 (4.59-39.2)	

* Statistical significance p <0.05; a: Chi square test; b: Fisher's exact test

Angle Q and Kujala

Graph 1 shows the correlation between the values of angle Q (right and left) and the total score of the test Kujala obtained in the initial population assessment (baseline), indicating that there is a negative correlation with a coefficient of Spearman's correlation $r = -0.415$ (moderate correlation) for the right Q angle and $r = -0.326$ (slight correlation) for the left Q angle, which means that when the values of the angle Q are greater, the total score in the Kujala test is lower.

Graph 1: Correlation of Q angle values on anterior knee pain with the Kujala test in the baseline.

[figure not shown]

Source: Author.

Angle Q and EVA

In Figure 2 a positive correlation, indicating that as the value of angle Q is greater, the score in the pain measured with a visual analog scale (VAS) is higher for both lower limbs, with a coefficient is observed of Spearman correlation of $r = 0.175$ for the right Q angle and $r = 0.216$ for the left Q angle. It should be noted that although the sample was small, there is a slight correlation.

Graph 2: Correlation of Q angle values on anterior knee pain with EVA in the baseline.

[figure not shown]
Source: Author.

Angle Q - Intervention Groups

In **graphs 3 and 4**, a negative correlation is shown between the values of the angle Q of the right and left knee by treatment groups (A and B) measured at the beginning of the intervention, and the total score obtained in the Kujala test, which indicates that as the angle Q increases, the total Kujala score decreases, with a moderate correlation for group A ($r = -0.545$ right knee) and ($r = -0.548$ left knee) and mild for group B ($r = -0.284$ right knee and $r = -0.173$ left knee).

[figure not shown]
Graph 3: Correlation of the values of the angle Q on the anterior pain of the right knee in the baseline, by treatment groups.

Therapeutic Effect of Two Muscle Strengthening Programs in Patients with Patellofemoral Pain Syndrome

Source: Author.

Graph 4: Correlation of Q angle values on left anterior knee pain in the baseline, by treatment groups.

Source: Author

Angle Q and Muscular Length

To determine the influence of muscle length (quadriceps, hamstrings, of tensioner of the fascia lata and gastrocnemius) on the alignment of the patella, in **Table 7**, the influence of muscle length on patellar alignment is observed, highlighting that the Right angle Q for people with a positive Ober

Therapeutic Effect of Two Muscle Strengthening Programs in Patients with Patellofemoral Pain Syndrome test (which evaluates the muscle length of tensioner of the fascia lata), obtained an average of 17.26 while for the left Q angle was 18.07 with one and one standard deviation of 3.88 and 4.11 respectively, indicating that those people with decreased muscle length, that is, a positive Ober test, had a higher Q angle compared to those who obtained a negative test. In the same way, a similar effect is observed in the 90-90 test which evaluates the muscle length of the hamstrings, because when the test is negative, that is, there is less muscle retraction, the angle Q is smaller, indicating lesser mal patellofemoral alignment.

Table 7: Influence of muscle length on the alignment of the patella

[figure not shown]
Test	Q angle	
	Straight Half of)	Left Half of)
Ober		
Positive	17.26 (3.88)	18.07 (4.11)
Negative	16.28 (3.51)	16.96 (3.82)
90-90		
Positive	17,02 (3,81)	17,32 (3.90)
Negative	15.0 (0.00)	-
ELY ^a	0.30	0.12
Lunge ^{to}	0.20	-0.08

a: Spearman correlation coefficient

Now, **Figure 5**, highlights the relationship between the muscle length of the quadriceps and the gastrocnemius, measured in degrees and centimeters respectively, and the bilateral Q angle of knees, indicating that there is a positive correlation for both knees in the Ely test, and for the right knee in the Lunge test, this correlation being slight, which suggests that when the muscle length is greater, the angle Q is smaller, whereas for the left knee in the Lunge test, the correlation was negative (-0.08), classified as very mild.

Figure 5: Relationship of muscle length using the Ely and Lunge tests on the bilateral Q angle of the knees.

Therapeutic Effect of Two Muscle Strengthening Programs in Patients with Patellofemoral Pain Syndrome

Source: Author.

Post-Intervention Results

To evaluate the effect of muscle strength on the alignment of the knees and analyze the effect of muscle strength on the unipodal balance, **Table 8** shows the deltas of the medians (changes or differences observed after the intervention) for each of the treatment groups and for each of the variables measured at the beginning and end of the intervention.

In this way, when they include or add exercises for the strengthening of the core, to the traditional treatment of SPF or anterior knee pain, the quality of life measured with the Kujala test in these patients increases, especially by the significant reduction of pain, highlighting for example, that for the total score of the Kujala test, there was a statistically significant difference ($p = 0.025$), with an increase of 5 points for group A (group A = 23.0, group B = 17.0), which indicates that the population of the study group improved their quality of life more after the intervention compared with the people of group B. A similar effect is observed in the increase of the strength of the core musculature for group A, especially in the oblique force evaluated with the side plate, with a difference of 30 seconds for group A, and only five seconds for group B on the left lateral plate, with a statistically significant p value (<0.001).

Therapeutic Effect of Two Muscle Strengthening Programs in Patients with Patellofemoral Pain Syndrome
On the other hand, the differences for the total pain evaluated with EVA were -6 and -4 for group B, with an interquartile range (-10; -4) and (-7; -3) respectively. Although p was not statistically significant, these differences were clinically relevant. For the hip and knee muscle strength, measured with the squat test, there was no statistically significant difference in the median of the deltas between the treatment groups, but there was one in each group, which means that all of them increased strength muscle in hips and knees, as a result of strengthening for these muscle groups.

Table 8: Effect of muscle strengthening on pain, knee alignment, core, hip and knee strength and balance by treatment groups.

Variable	Treatment A			Treatment B			Value p *
	Initial Medium (RI)	Final Medium (RI)	Delta Medium (RI)	Initial Medium (RI)	Final Medium (RI)	Delta Medium (RI)	
Pain (EVA)	7.5 (5.5-9.0)	2 (0-2)	-6 (-10; -4)	7.0 (5.5-8.5)	2.0 (0-4)	-4 (-7; -3)	0.058
Kujala total test score	65.5 (42.5-72.5)	88.0 (81.0-95.0)	23.0 (16.0-37.0)	53.0 (44.5-71.5)	78.0 (64.0-88.0)	17.0 (8.0-24.0)	0.025
Squats	10.0 (8.0-18.5)	35.0 (30.0-38.0)	20.0 (18.0-25.0)	12.5 (8.5-20.0)	35.0 (29.0-38.0)	20.0 (15.0-24.0)	0.670
IPAQ (minutes)	3003 (1116-4638)	4275 (2587-6522)	1539 (807-2457)	1617 (944-6138)	4598 (2888-7344)	1977 (1191-2815)	0,492
Q angle							
Straight	19.0 (15.0-20.0)	18.0 (15.0-20.0)	0 (-2; 2)	18.0 (15.0-20.0)	18.0 (15.0-20.0)	0 (-2; 2)	0.819
Left	18.0 (15.0-20.0)	18.0 (16.0-20.0)	0 (-2; 2)	18.0 (15.0-20.0)	18.0 (15.0-20.0)	0 (-2; 2)	0.672

Balance with open eyes							
Straight	30.0 818.25- 45.0)	45.0 (45.0- 45.0)	11.5 (0- 25.5)	40.0 (18.25- 45.0)	45.0 (45.0- 45.0)	7.5 (0- 30.0)	0.916
Left	29.5 (15.75- 44.0)	45.0 (45.0- 45.0)	9.5 (0- 21.5)	25.75 (14.5- 45.0)	45.0 (45.0- 45.0)	20.0 (0- 30.0)	0.282
Balance with closed eyes							
Straight	4.5 (3.0- 9.259)	28.5 (21.0- 35.0)	20.0 (14.0- 27.5)	5.25 (3.0- 7.25)	23.5 (16.5- 31.5)	19.0 (9.5- 24.0)	0.671
Left	5.0 (3.0- 8.7)	30.0 (23.5- 38.0)	24.5 (13.0- 30.5)	4.25 (3.5- 7.259)	27.5 (14.0- 34.5)	20.0 (10.5- 30.5)	0.349
Griddle	20.5 (12.0- 32.0)	60.0 (45.0- 70.0)	37.0 (24.0- 48.0)	30.0 (13.5- 33.5)	35.0 (20.0- 60.0)	10.0 (2.0- 15.0)	<0.001
The t. Right	15.0 (10.0- 21.0)	45.0 (38.0- 51.0)	30.0 (19.0- 36.0)	15.0 (9.5- 20.0)	22.0 (16.0- 38.0)	6.0 (2.0- 12.0)	<0.001
The t. Left	12.5 (10.5- 19.0)	45.0 (36.0- 56.0)	30.0 (17.0- 40.0)	18.0 (11.0- 23.0)	21.0 (15.0- 34.0)	5.0 (-2 - 10.0)	<0.001
Trunk extension	13.5 (6.0- 26.5)	61.0 (50.0- 75.0)	49.0 (30.0- 55.0)	13.5 (2.5- 20.0)	30.0 (15.0- 60.0)	15.0 (7.0- 34.0)	0.001

* U of Mann-Whitney for the delta of the measurements between the groups.

He was also interested in this research, to observe the intra-group differences of including hip and knee muscle strengthening exercises (conventional physiotherapeutic treatment) performed in the same way for both intervention groups, as mentioned in the description of the strengthening protocol.

Intragroup differences

Therapeutic Effect of Two Muscle Strengthening Programs in Patients with Patellofemoral Pain Syndrome
In **Table 9**, differences in medians and interquartile ranges their entire study population at the beginning and end of treatment for muscle strength, pain and level of physical activity is. It can be seen that the gluteal and quadriceps muscle strength measured with the squat test at the end of the treatment was the same in both groups, with a statistically significant p value (<0.001), which means that the whole population increased strength in a significant way.

In the same way, a similar effect was observed in the median pain measured with the VAS at the end of the treatment, because they all reported a decrease in pain, this difference being statistically significant, with a p-value less than 0.001. However, in the measurement of physical activity level with the long IPAQ at the end of the treatment, it was observed that the study population in group B spent less time practicing physical activity at the beginning of treatment, but both groups increased in time similar this practice at the end of the treatment; however, this difference was not statistically significant.

Table 9: Difference of intragroup medians for muscle strength, pain and physical activity level.

Variable	Treatment A			Treatment B		
	Initial Medium (RI)	Final Medium (RI)	Value p *	Initial Medium (RI)	Final Medium (RI)	Value p *
Squats	10.0 (8.0-18.5)	35.0 (30.0-38.0)	<0.001	12.5 (8.5-20.0)	35.0 (29.0-38.0)	<0.001
IPAQ (minutes)	3003 (1116-4638)	4275 (2587-6522)	0.029	1617 (944-6138)	4598 (2888-7344)	0.012
Pain (EVA)	7.5 (5.5-9.0)	2.0 (0.0-2.0)	<0.001	7.0 (5.5-8.5)	2.0 (0-4)	<0.001

* Wilcoxon nonparametric test

Muscular Strength and Static Balance

In **Table 10**, the correlation between the muscle and gluteus muscle strength differences measured with the squat and unipodal balance test evaluated with the One Leg Stance test with open and closed eyes by treatment groups is shown, with which it is emphasized that, for both treatment groups, the unipodal balance improved clinically significant. However, for the study group (A), this correlation was greater (strong), especially in the variable with open eyes for both lower limbs, indicating that by increasing muscle strength (glutes and quadriceps in this case) it is improved the unipodal balance. Although there is an increase in the balance for both treatment groups, there is a stronger correlation when core exercises are included, which is what happens in group A.

Table 10: Correlation between differences in muscle strength and balance by treatment groups

Therapeutic Effect of Two Muscle Strengthening Programs in Patients with Patellofemoral Pain Syndrome

Variable	Squats	
Balance	Treatment A *	Treatment B *
Right with open eyes	0,558	0.121
Left with open eyes	0,554	0.110
Right with closed eyes	0.390	0.009
Left with closed eyes	0.008	-0.244

* Spearman correlation coefficient.

With the previously stated results, the alternative hypothesis of this study is rejected, which means that adding core exercises to traditional hip and knee muscle strengthening for the treatment of anterior knee pain in patients diagnosed with SPF is more effective in reducing pain and improving the quality of life of these people, they do only hip and knee strengthening exercises.
